6.3. Lifestyle and/or Dietary Requirements

Throughout the study, subjects may undergo medical assessments and review of compliance with requirements before continuing in the study.

6.3.1. Meals and Dietary Restrictions

Standardized meals will be provided during each subject's stay in the CRU.

Subjects will be required to fast overnight (at least 8 hours) prior to study drug doses that are followed by PK sample collection (Period 1 Day 1 and Period 2 Days 7 and 8). Fluids will be restricted from 1 hour prior to and until 1 hour after dosing with the exception of water required

for study drug administration. Water will be allowed ad libitum at all other times during the study. A standard meal will be given to the subjects no sooner than 4 hours after dosing on Period 1 Day 1 and Period 2 Days 7 and 8. On all other days when dosing is not followed by PK sample collection, study drug may be administered without regard to food and water. Meals will be provided as appropriate at all other times.

Subjects will refrain from consuming grapefruits or grapefruit-containing products, Seville oranges or Seville orange-containing products, star fruits or star fruit-containing products, pomelo, or commercial apple juice or orange juice within 7 days prior to the first dose of any study drug until the final PK sample is collected. If this situation arises, inclusion or ongoing participation of the subject may be at the discretion of the investigator, in consultation with the sponsor or designee.

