3.2.1.1. Clinical Pharmacokinetic Data

LY3314814 PK have been evaluated following single doses of 1 to 750 mg and at steady state from 15 to 150 mg. Following oral dosing, LY3314814 t_{max} is approximately 1 to 2 hours postdose and then follows a bi-exponential elimination profile. The LY3314814 $t_{1/2}$ is approximately 18 hours. Upon multiple dosing, exposure increases modestly with an accumulation ratio of approximately 1.46, based on area under the drug concentration-time curve (AUC). Steady state appears to be achieved 4 to 8 days following the initiation of dosing, consistent with LY3314814 $t_{1/2}$. Over the dose range from 15 to 150 mg, the AUC of LY3314814 increases in a dose proportional manner, although C_{max} appears to increase in a greater-than-proportional manner (a 3.3-fold increase in dose produced approximately a 4.2-fold increase in $C_{ss,max}$ values). No meaningful differences in PK have been observed between young and elderly healthy subjects, or between healthy subjects and patients with AD. Renal clearance was approximately 1.0 to 1.5 L/h (roughly 5% to 10% of apparent total body clearance), suggesting that renal clearance is a minor elimination pathway. LY3314814 is a substrate of CYP3A, as shown by drug interaction studies where strong inhibitors of CYP3A activity increased LY3314814 exposure by up to 2.85-fold. While LY3314814 was shown to be

a CYP3A inducer in vitro, clinical evidence suggests that there is no meaningful effect of LY3314814 on CYP3A activity. The effect of LY3314814 on Pgp activity has been studied in vitro and clinically. In vitro studies demonstrate that LY3314814 is a substrate and an inhibitor of Pgp. In clinical studies, LY3314814 increased dabigatran exposures by 15% when LY3314814 and dabigatran etexilate were administered at the same time, demonstrating that LY3314814 is a relatively weak inhibitor of Pgp. Since 21 June 2016, a food effect study was completed demonstrating that administration of 50 mg LY3314814 with food resulted in a modest (approximately 17%) reduction in C_{max} , although AUC was not impacted, suggesting that food reduces the rate, but not the extent of absorption. The PK results for the major metabolite AZ13569724 mirrored those of the parent.

Additional information regarding LY3314814 PK may be found in the Investigator's Brochure (IB).

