7.2.1. Selection and Timing of Doses

Doses administered on the mornings of Period 1 Day 1 and Period 2 Days 7 and 8 will be preceded by an overnight fast of at least 8 hours and followed by a fast of at least 4 hours postdose. See Section 6.3.1 for meal and dietary restrictions. All doses will be administered at approximately the same times on each day. The actual time of all dose administrations will be recorded in the subject's electronic case report form (eCRF).

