6. TREATMENTS

The following is a list of the study treatment names that will be used in the safety TFLs.

Study Treatment Name	Treatment order in TFL
20 mg rosuvastatin (D1)	1
50 mg LY3314814 QD (D1 – D7)	2
50 mg LY3314814 QD + 20 mg rosuvastatin (\geq D8)	3

D = Day

The following is a list of the study treatment names that will be used in the PK TFLs.

Study Treatment Name	Treatment order in TFL
20 mg rosuvastatin	1
50 mg LY3314814 QD + 20 mg rosuvastatin	2
50 mg LY3314814 QD	3

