9.4.4 Vital signs

Vital signs data will be summarized by treatment together with changes from baseline, where baseline is defined as Day 1 predose of each period. Figures of mean vital signs and mean

changes from baseline profiles by treatment will be presented by treatment. Furthermore, values for individual subjects will be listed.

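### Period 2 Day 1, the only LY3314814-alone vital-sign profile and the Period 2 baseline, has no food or fluid rule around dosing, while the two profile days compared with it are fasted

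*Protocol*

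**What the plan says.** **Food and fluid.** Protocol 7.2.1 names the fasted days: "Doses administered on the mornings of Period 1 Day 1 and Period 2 Days 7 and 8 will be preceded by an overnight fast". Protocol 6.3.1 names the same three days, restricts fluids from 1 h before to 1 h after dosing, and delays the first meal: "A standard meal will be given to the subjects no sooner than 4 hours after dosing". For the remaining dosing days it adds: "On all other days when dosing is not followed by PK sample collection, study drug may be administered without regard to food and water". Period 2 Day 1 has no PK sample, so it is one of these days. Meals in the unit are otherwise described only in general terms: "Standardized meals will be provided during each subject's stay in the CRU".

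**Vital signs.** The Schedule of Activities places timed supine and orthostatic readings (predose, 4, 8 and 12 h, with 24 h on the next day) on Period 1 Day 1, Period 2 Day 1 and Period 2 Day 8. Read by column position, it has none on Period 2 Days 3 to 7.

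**Analysis.** SAP 6 labels Period 2 Days 1 to 7 as LY3314814 alone, and Day 8 onward as the combination. SAP 9.4.4 summarises and plots vital signs by treatment, with change from baseline, "where baseline is defined as Day 1 predose of each period". Protocol 10.3.1.2 adds that orthostatic change is assessed from supine to standing. SAP 9.4.8 plans no inferential safety analysis.

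**The concern.** Each treatment has one timed vital-sign profile. The LY3314814-alone profile falls on the one profile day where neither meals nor fluids are tied to the dose. The fasted LY3314814-alone day, Period 2 Day 7, has no scheduled vital signs and cannot stand in for it. The Period 2 Day 1 predose reading also serves as baseline for everything in Period 2.

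If eating or drinking moves blood pressure or pulse, that movement is displayed as a difference between treatments, and the planned summaries cannot take it out. The issue deserves attention because Protocol 3.2.1.2 lists orthostatic hypotension among the most frequent related events in healthy subjects, and safety of the coadministration is a secondary objective. The protocol fixes the food state where PK samples are drawn but not on this matching safety day.

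**Working it through.** The plan gives no figure to reproduce: no passage describes an effect of food on blood pressure or pulse. The check sets the schedule against the food rules and then traces where a shift would go.

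**Step 1. The three profile days**

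| Profile day | Treatment | Food and fluid rule around dosing | Baseline used |
|---|---|---|---|
| Period 1 Day 1 | rosuvastatin alone | fasted to at least 4 h; fluids held ±1 h | own predose, fasted |
| Period 2 Day 1 | LY3314814 alone | none | own predose, food state not set |
| Period 2 Day 8 | combination | fasted to at least 4 h; fluids held ±1 h | Period 2 Day 1 predose |

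On the fasted days the first meal comes no sooner than 4 h, so the rule separates the days at predose and 4 h. By 8 h meals are allowed on all three days, so the 8, 12 and 24 h readings themselves are little affected.

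**Step 2. Assumed quantities (none is in the documents)**

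- d: the shift in a reading when fed rather than fasted, taken as equal at predose and 4 h for simplicity; it may be zero.
- p0: the share of subjects already fed at the Period 2 Day 1 predose reading.
- p4: the share fed by the 4 h reading that day, so p4 is at least p0.

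**Step 3. Bias in each mean at 4 h**

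- Rosuvastatin alone: raw 0; change 0.
- LY3314814 alone: raw p4·d; change p4·d − p0·d.
- Combination: raw 0; change 0 − p0·d = −p0·d.

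**Step 4. Bias in each contrast at 4 h**

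- Combination minus LY3314814 alone: raw −p4·d; change −p0·d − (p4 − p0)·d = −p4·d. The shared baseline cancels.
- Combination minus rosuvastatin alone: raw 0; change −p0·d.
- LY3314814 alone minus rosuvastatin alone: raw p4·d; change (p4 − p0)·d.

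**Step 5. Range**

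| Period 2 Day 1 practice | Combination − LY3314814 alone (raw or change) | Combination − rosuvastatin alone (change) | LY3314814 alone − rosuvastatin alone (change) |
|---|---|---|---|
| all fasted through 4 h (p0 = p4 = 0) | 0 | 0 | 0 |
| all fed after predose, before 4 h (p0 = 0, p4 = 1) | −d | 0 | d |
| all fed before predose (p0 = p4 = 1) | −d | −d | 0 |

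Change from baseline at 8 to 24 h still carries −p0·d in any Period 2 contrast with rosuvastatin alone, because the baseline is subtracted at every time point.

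**Step 6. Orthostatic difference**

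Write the shift as d_sup for supine and d_st for standing. Standing minus supine then shifts by d_st − d_sup, and the 4 h contrast of combination with LY3314814 alone carries −p4·(d_st − d_sup). Any part common to both postures drops out. The supine-to-standing difference needs no Day 1 baseline unless its change from baseline is also shown.

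**The case against.** The case for leaving the plan alone is substantial, and most of it stands.

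- Feeding on Period 2 Day 1 is permitted, not required. No passage says that subjects eat before the predose reading. Meals are standardised, only meals provided by the unit may be eaten, and dose times are about the same each day. All subjects might in practice be fasted at predose, and the bias would then be confined to 4 h or absent.
- Water is free on all three days outside the 1 h window around dosing, so the fluid rule cannot separate the days at 4 h in respect of water.
- The secondary safety endpoints are the incidence of TEAEs and SAEs, not vital-sign change. Protocol 9.4.2 asks for unscheduled orthostatic readings, if possible, during dizziness or postural symptoms.
- Food is not the only difference between the days. Period 2 Day 1 is a first dose and Day 8 is near steady state, with accumulation of about 1.46 on AUC (Protocol 3.2.1.1), and the sequence is fixed. Matching the meals leaves these in place.

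Two stronger readings are tempting. A reader might infer from Protocol 3.2.1.1, where dosing "with food resulted in a modest (approximately 17%) reduction" in LY3314814 Cmax, that lower exposure distorts the Day 1 profile. The same section says AUC was unaffected and puts tmax at 1 to 2 h, while the first postdose reading is at 4 h, so the figure says little about any scheduled reading. A reader might also assume a shift and an SD in mmHg and express the bias in standard errors. The documents supply neither quantity, and the summaries are descriptive.

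The objection does not remove the basic fact: the plan leaves the food state open on one of three profile days and does not require it to be recorded. Protocol 7.2.1 sends dose times to the eCRF but does not mention meal times.

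**Conclusion.** The point holds as a minor, avoidable weakness in the by-treatment vital-sign summaries. At 4 h the contrast of combination with LY3314814 alone can be biased by between zero and d in size. Change-from-baseline contrasts with rosuvastatin alone can be biased by up to d through the Period 2 predose value. Where in that range the bias falls depends on d and on how many subjects were fed at each reading, and the documents give neither.

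A reader might infer that the whole comparison of LY3314814 alone with the combination is spoiled, and through the baseline as well. The documents do not support that. The baseline is shared and cancels in that contrast, the 8 to 24 h readings are little affected, and the orthostatic difference keeps only the part of the shift that differs between postures. The primary rosuvastatin AUC analysis is unaffected.

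The conclusion assumes that the vital-sign days have been read correctly by column position from the Schedule of Activities.

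**What to change.** **Protocol.** Reconcile Sections 6.3.1 and 7.2.1 with the vital-sign schedule so that Period 1 Day 1, Period 2 Day 1 and Period 2 Day 8 share the same food and fluid condition from before the predose reading through the 4 h reading. The Schedule allows ±10% on postdose times, so the 4 h reading may fall between 3.6 and 4.4 h (4 ± 0.4), on either side of a meal given at 4 h. State the order of meal and reading, and keep it the same on all three days.

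**Subjects already dosed.** Report the Period 2 Day 1 food state if source documents hold it. If meal times were not kept, or all subjects followed one timetable, no comparison by food state is possible and only the limitation can be stated.

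**Report.** When interpreting the SAP 9.4.4 summaries, say that LY3314814 alone and the combination may differ in food state at 4 h, that the Period 2 baseline may differ from the Period 1 baseline in the same way, and that first dose versus near steady state and the fixed sequence also separate the treatments.

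**Cost.** One more morning of controlled meals for subjects already resident in the unit, a short protocol change and a few sentences in the report. No procedure is added.

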6.3.2. Caffeine, Alcohol, and Tobacco

Subjects will refrain from consuming caffeine- or xanthine-containing food and drinks within 48 hours prior to Check-in. Caffeine- or xanthine-containing food and drinks will not be allowed while subjects are resident at the CRU.

Alcohol will not be permitted from 48 hours prior to Check-in and during the study.

Smoking will not be permitted throughout the study. Subjects will not have used any tobacco- or nicotine-containing products (including, but not limited to, cigarettes, pipes, cigars, chewing tobacco, nicotine patches, nicotine lozenges, or nicotine gum) within 3 months prior to Check-in and during the entire study.

6.3.3. Activity

No strenuous exercise will be allowed for 48 hours prior to the first dose and during the study.

6.4. Screen Failures

Individuals who do not meet the criteria for participation in this study (screen failure) will not be re-screened.

7. Treatment

7.1. Treatment Administered

Table AZEB.2 shows the treatment regimens.

Tablets of LY3314814 and/or rosuvastatin will be administered orally with approximately 240 mL of room temperature water in the morning in a sitting position. Subjects will not be allowed to lie supine for 2 hours after dosing, unless clinically indicated or for study procedures.

Table AZEB.2. Treatments Administered

Treatment Name	Rosuvastatin	LY3314814
Dosage Formulation	20-mg tablet	50-mg tablet
Dosage Level	20 mg	50 mg
Route of Administration	Oral	Oral
Dosing Instructions	1 tablet taken on Period 1 Day 1 and Period 2 Day 8	1 tablet taken once daily on Period 2 Days 1 through 12

The investigator or designee is responsible for:

- explaining the correct use of the investigational products to the site personnel,
- verifying that instructions are followed properly,
- maintaining accurate records of investigational product dispensing and collection,
- and returning all unused medication to Lilly or its designee at the end of the study.

Note: In some cases, sites may destroy the material if, during the investigative site selection, the evaluator has verified and documented that the site has appropriate facilities and written procedures to dispose of clinical trial materials.

7.1.1. Packaging and Labeling

Each LY3314814 tablet is oval, biconvex, plain, dark tan, and film-coated. Tablets contain 50 mg LY3314814 and excipients and are provided in high-density polyethylene bottles.

Each rosuvastatin tablet is round, biconvex, pink, coated, and debossed with “CRESTOR” and “20” on one side (Crestor Prescribing Information). Tablets contain 20 mg rosuvastatin and excipients and are provided in bottles.

Clinical trial materials will be labeled according to the country’s regulatory requirements.

7.2. Method of Treatment Assignment

This study is not randomized. All subjects are to receive all treatments as described in Section 5.1.

7.2.1. Selection and Timing of Doses

Doses administered on the mornings of Period 1 Day 1 and Period 2 Days 7 and 8 will be preceded by an overnight fast of at least 8 hours and followed by a fast of at least 4 hours postdose. See Section 6.3.1 for meal and dietary restrictions. All doses will be administered at approximately the same times on each day. The actual time of all dose administrations will be recorded in the subject's electronic case report form (eCRF).

7.3. Blinding

This is an open-label study.

7.4. Dose Modification

Dose adjustments are not allowed for this study.

7.5. Preparation/Handling/Storage/Accountability

Only participants enrolled in the study may receive investigational product and only authorized site staff may supply or administer study treatment. All study treatments should be stored in an environmentally controlled and monitored (manual or automated) area in accordance with the labeled storage conditions with access limited to the investigator and authorized site staff.

The investigator, institution, or the head of the medical institution (where applicable) is responsible for study treatment accountability, reconciliation, and record maintenance (such as receipt, reconciliation, and final disposition records).

7.6. Treatment Compliance

The investigational product will be administered at the clinical site, and documentation of treatment administration will occur at the site.

7.7. Concomitant Therapy

Drugs that are known strong inducers or inhibitors of CYP3A, strong inhibitors of Pgp, or inducers or inhibitors of BCRP are specifically excluded. Drugs or dietary supplements that may affect rosuvastatin are specifically excluded. Additional drugs are to be avoided during the study unless required to treat an AE or for the treatment of an ongoing medical problem.

If the need for concomitant medication arises, inclusion or continuation of the subject may be at the discretion of the investigator after consultation with a Lilly clinical pharmacologist (CP) or clinical research physician (CRP). Occasional acetaminophen (paracetamol) up to a 2-gram total dose in a 24-hour period may be used at the discretion of the investigator. Any additional medication used during the course of the study must be documented.

7.8. Treatment after the End of the Study

Not applicable for this study.

8. Discontinuation Criteria

8.1. Discontinuation from Study Treatment

Discontinuation of the investigational product for abnormal liver tests **should be considered** by the investigator when a subject meets one of the following conditions after consultation with the Lilly-designated medical monitor:

- ALT or AST >5 times ULN
- ALT or AST >3 times ULN along with one of the following criteria :
 - sustained for more than 2 weeks, or
 - total bilirubin level (TBL) >2 times ULN, or
 - prothrombin time >1.5 times ULN, or
 - the appearance of fatigue, nausea, vomiting, right upper-quadrant pain or tenderness, fever, rash, and/or eosinophilia (>5%)
- Alkaline phosphatase (ALP) >3 times ULN
- ALP >2.5 times ULN and TBL >2 times ULN
- ALP >2.5 times ULN with the appearance of fatigue, nausea, vomiting, right quadrant pain or tenderness, fever, rash, and/or eosinophilia (>5%)

Subjects who discontinue treatment due to a hepatic event or abnormality of liver tests should have further clinical and laboratory monitoring and should have additional data collected. The process should be initiated by the investigator in consultation with the Lilly CRP/CP.

Subjects who discontinue the investigational product early will have early discontinuation procedures performed as shown in the Schedule of Activities (Section 2).

8.1.1. Discontinuation of Inadvertently Enrolled Subjects

If the sponsor or investigator identifies a subject who did not meet enrollment criteria and was inadvertently enrolled, a discussion must occur between the Lilly CP or CRP and the investigator to determine if the subject may continue in the study. If both agree it is medically appropriate to continue, the investigator must obtain documented approval from the Lilly CP or CRP to allow the inadvertently enrolled subject to continue in the study with or without continued treatment with investigational product.

8.2. Discontinuation from the Study

Subjects will be discontinued in the following circumstances:

- enrollment in any other clinical trial involving an investigational product or enrollment in any other type of medical research judged not to be scientifically or medically compatible with this study

- participation in the study needs to be stopped for medical, safety, regulatory, or other reasons consistent with applicable laws, regulations, and good clinical practice (GCP)
- investigator decision
 - the investigator decides that the subject should be discontinued from the study
- subject decision
 - the subject requests to be withdrawn from the study

Subjects who discontinue the study early will have early discontinuation procedures performed as shown in the Schedule of Activities (Section 2).

8.3. Subjects Lost to Follow-up

A subject will be considered lost to follow-up if he or she repeatedly fails to return for scheduled visits and is unable to be contacted by the study site. Site personnel are expected to make diligent attempts to contact subjects who fail to return for a scheduled visit or were otherwise unable to be followed up by the site.

9. Study Assessments and Procedures

Section 2 lists the Schedule of Activities, detailing the study procedures and their timing (including tolerance limits for timing).

Appendix 2 lists the clinical laboratory tests that will be performed for this study.

Appendix 5 provides a summary of the maximum number and volume of invasive samples, for all sampling, during the study.

Unless otherwise stated in subsections below, all samples collected for specified laboratory tests will be destroyed within 60 days of receipt of confirmed test results. Certain samples may be retained for a longer period, if necessary, to comply with applicable laws, regulations, or laboratory certification standards.

Investigators must document their review of each laboratory safety report.

9.1. Efficacy Assessments

This section is not applicable for this study.

9.2. Adverse Events

Investigators are responsible for monitoring the safety of subjects who have entered this study and for alerting Lilly or its designee to any event that seems unusual, even if this event may be considered an unanticipated benefit to the subject.

The investigator is responsible for the appropriate medical care of subjects during the study.

The investigator remains responsible for following, through an appropriate health care option, AEs that are serious or otherwise medically important, considered related to the investigational product or the study, or that caused the subject to discontinue the investigational product before completing the study. The subject should be followed until the event resolves, stabilizes with appropriate diagnostic evaluation, or is reasonably explained. The frequency of follow-up evaluations of the AE is left to the discretion of the investigator.

After the informed consent form (ICF) is signed, study site personnel will record, via eCRF, the occurrence and nature of each subject's preexisting conditions. Additionally, site personnel will record any change in the condition(s) and the occurrence and nature of any AEs.

Any clinically significant findings from ECGs, labs, vital sign measurements, and other procedures should be reported as an AE to Lilly or its designee.

The investigator will interpret and document whether or not an AE has a reasonable possibility of being related to study treatment or a study procedure, taking into account concomitant treatment or pathologies.

A "reasonable possibility" means that there is a cause and effect relationship between the investigational product and/or study procedure and the AE.

Planned surgeries should not be reported as AEs unless the underlying medical condition has worsened during the course of the study.

If a subject's investigational product is discontinued as a result of an AE, study site personnel must report this to Lilly or its designee via eCRF.

